12.1.3 Exploratory Endpoints

Any comparisons between groups (Cingal, Monovisc, TH), within groups and / or time points (from baseline through to 39 weeks) not described in the primary or secondary endpoints may be presented

in the exploratory endpoints including:

- EuroQoL (EQ-5D)
- WOMAC Pain Score (100mm VAS)
- OMERACT-OARSI
- Total WOMAC
- WOMAC Stiffness Score
- WOMAC Physical Function Score
- Patient Global Assessment
- Evaluator Global Assessment
- Range of Motion
- Rescue Medication Usage: Difference in analgesic use measured by number of pills taken between visits will be compared between treatment groups descriptively.
- Number of Subjects Considered Treatment Failures: Treatment Failure: A subject who undergoes a procedure or uses a medication (other than the rescue medication) for the treatment of OA in the index knee at any time after the study injection through the 39 week visit.

For the exploratory analyses, the continuous variables will be analyzed via an analysis of variance and contrasts used to assess the prescribed comparisons. For the discrete variables, a Fisher's exact test will be used to assess the desired comparisons.

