4.1.3 Secondary Efficacy Endpoints

There are multiple secondary endpoints. In order to preserve the integrity of the Type I error, these will be tested in a hierarchical manner. The order of the testing is as the order presented here.

The change from baseline in knee pain as measured by the WOMAC Pain Score (100 mm VAS) at 39 weeks post treatment comparing the Cingal group to the TH group.

This secondary efficacy endpoint is the change from baseline in knee pain as measured by the WOMAC Pain Score (100 mm VAS) at 39 weeks post treatment comparing the Cingal group to the TH group.

Data will be analyzed via an analysis of variance (ANOVA) with a term for treatment and baseline pain score as a covariate. The primary hypothesis will be tested by a predefined contrast for comparing the Cingal group to the triamcinolone hexacetonide group. Formally, the hypothesis to be tested is:

$$H_0: \mu_{DC} = \mu_{DT} \text{ versus } H_A: \mu_{DC} \neq \mu_{DT}.$$

Where μ_{DC} is the mean change from baseline in the WOMAC Pain Score for the Cingal group at 39 weeks and μ_{DT} is the mean change from baseline in the WOMAC Pain Score for the triamcinolone hexacetonide group at 39 weeks. Since there are three treatment groups in this study, this hypothesis will be tested using a one way ANOVA and constructing a contrast for this hypothesis. This process is the same as using a baseline pain adjusted two-sample t-test with the common variance estimate from the ANOVA.

The anticipated SAS code for this analysis is given as:

The mean difference will be estimated and tested using the contrasts from PROC GLM on the responses at the 39 week time period.

```

PROC GLM DATA=EFF;
  WHERE VISITNO = 39;
  CLASS TRT;
  MODEL WOMODIFF = BASEWOM TRT / TYPE3 ALPHA=0.05;
  ESTIMATE 'CINGAL VS MONOVISC' TRT 1 -1 0 ;
  ESTIMATE 'CINGAL VS TH'      TRT 1 0 -1 ;
  ESTIMATE 'MONOVISC VS TH'    TRT 0 1 -1 ;
  LSMEANS TRT / DIFF CL ALPHA=0.05;
  FORMAT TRT TRTF. ;
  RUN;

```

In this model, the WOMODIFF is the difference in WOMAC Pain Scores from baseline. The variable TRT is a categorical variable where 1 = Cingal, 2=Monovisc, and 3=TH. The variable

BASEWOM is the baseline WOAMC scores and the variable VISITNO is the visit number identifier. ODS statements will be used to output the contrasts and the mean differences into data sets that can be easily displayed using PROC REPORT. The primary analysis will be comparing Cingal to TH.

The tables for this analysis will be displayed as:

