Data will be analyzed via an analysis of variance (ANOVA) with a term for treatment and baseline Total WOMAC score as a covariate. The hypothesis will be tested by a predefined contrast for comparing the Cingal group to the TH group. Formally, the hypothesis to be tested is:

$H_0: \mu_{DC} = \mu_{DT}$ versus $H_A: \mu_{DC} \neq \mu_{DT}$.

Where μ_{DC} is the mean change from baseline in the Total WOMAC Score for the Cingal group at 39 weeks and μ_{DT} is the mean change from baseline in the Total WOMAC Score for the TH group at 39 weeks.

The change from baseline in the Patient Global Assessment at 39 weeks post treatment comparing the Cingal group to the triamcinolone hexacetonide group.

Since this is a secondary endpoint the data will be analyzed for each time point individually with no adjustment for multiplicity. Data will be analyzed via an analysis of variance with a term for treatment and baseline PGA score as a covariate. The primary hypothesis will be tested by a predefined contrast for comparing the Cingal group to the Triamcinolone Hexacetonide group. Formally, the hypothesis to be tested is:

$H_0: \mu_{DC} = \mu_{DT}$ versus $H_A: \mu_{DC} \neq \mu_{DT}$.

Where μ_{DC} is the mean change from baseline in the Patient Global Assessment Score for the Cingal group and μ_{DT} is the mean change from baseline in the Patient Global Assessment Score for the triamcinolone hexacetonide group. Since there are three treatment groups in this study, this hypothesis will be tested using a one way ANOVA and constructing a contrast for this hypothesis. This process is the same as using a two-sample t-test with the common variance estimate from the ANOVA.

The mean difference will be estimated and tested using the contrasts from PROC GLM on the responses by week with the 39 week time period being the time point of interest for the analysis of this secondary endpoint.

4.1.3.4 The change from baseline in the Evaluator Global Assessment through 39 weeks post treatment comparing the Cingal group to the triamcinolone hexacetonide group.

Since this is a secondary endpoint the data will be analyzed for each time point individually with no adjustments for multiplicity. Data will be analyzed via an analysis of variance with a term for treatment and baseline EGA score as a covariate. The primary hypothesis will be tested by a predefined contrast for comparing the Cingal group to the triamcinolone hexacetonide group. Formally, the hypothesis to be tested is:

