4.1.4 Exploratory Endpoints

Any comparisons between groups (Cingal, Monovisc, TH), within groups and / or time points (from baseline through to 39 weeks) not described in the primary or secondary endpoints may be presented in the exploratory endpoints including:

- EuroQoL (EQ-5D)
- WOMAC Pain Score (100mm VAS)
- OMERACT-OARSI
- Total WOMAC
- WOMAC Stiffness Score
- WOMAC Physical Function Score
- Patient Global Assessment
- Evaluator Global Assessment
- Range of Motion
- Rescue Medication Usage: Difference in analgesic use measured by number of pills taken between visits will be compared between treatment groups descriptively.
- Number of Subjects Considered Treatment Failures: Treatment Failure: A subject who undergoes a procedure or uses a medication (other than the rescue medication) for the treatment of OA in the index knee at any time after the study injection through the 12 week visit.

For the exploratory analyses, the continuous variables will be analyzed via an analysis of variance and contrasts used to assess the prescribed comparisons. For the discrete variables, a Fisher's exact test will be used to assess the desired comparisons.

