4.2 STATISTICAL METHODS

Tabulation of summary statistics, graphical presentations, and statistical analyses will be performed using SAS® software 9.1.3 or higher version. Where not otherwise specified, the last pre-treatment observation will be used as baseline for calculating post-treatment changes from baseline. The primary presentations and analyses will be based on data pooled across study centers. Relevant summaries for individual centers, or combinations of centers, may be presented for primary data. All testing and confidence intervals will use a significance level of 5%.

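### The exploratory methods sections allow within-group comparisons between visits but give only Fisher's exact test and ANOVA contrasts, with no paired method for same-subject data

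*SAP*

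**What the plan says.** SAP 4.1.4 (Exploratory Endpoints), matched by Protocol 12.1.3, opens the exploratory analyses to comparisons "within groups and / or time points (from baseline through to 39 weeks) not described in the primary or secondary endpoints may be presented". The list includes OMERACT-OARSI response, the WOMAC scores, both global assessments, range of motion and EQ-5D. Two sentences then assign methods without exception: "the continuous variables will be analyzed via an analysis of variance and contrasts used to assess the prescribed comparisons", and "For the discrete variables, a Fisher's exact test will be used to assess the desired comparisons".

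Elsewhere in the plan:
- SAP 4.1.3 describes its contrasts for the Patient Global Assessment in these terms: "This process is the same as using a two-sample t-test with the common variance estimate from the ANOVA".
- The only ANOVA code in the SAP selects one visit ("WHERE VISITNO = 39"), takes change from baseline as the response, and has treatment as its only class variable. It has no subject or visit term.
- GEE appears in SAP 4.6 and Protocol 12.6, for discrete variables when additional factors are brought into the model.
- Mixed-effects repeated-measures methods appear in SAP 4.5 and Protocol 12.5, in connection with missing data.

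No section names a paired or repeated-measures test for exploratory comparisons between visits.

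**The concern.** The Protocol 10.1 schedule assesses the same subjects at every visit, and 16-02 data carry forward into 17-02. Responder status or a WOMAC score at two visits in one arm is therefore paired data. The question is whether the marginal rate or mean changed in those subjects. Fisher's exact test on two stacked visits, or a two-sample contrast between visits, treats them as different people and ignores the within-subject covariance. The p-value and the interval for the visit-to-visit difference are then wrong. A non-significant result could reflect the choice of test more than an absence of change.

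**Working it through.** **Inputs from the documents.** Two-sided 5% level (SAP 4.2 and the hypotheses in 4.1.2 and 4.1.3); SD 20 mm; planned arms of 256, 256 and 64 (SAP 4.1.1, Protocol 12.1).

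**Assumptions, not in the documents.** Within-subject correlation (ρ for continuous data, φ for binary) from 0 to 0.7; responder rates of 70% and 60%; visit-to-visit changes of 3 and 5 mm; every subject observed at both visits.

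**1. The plan's own figure.** No operating characteristic is stated for the exploratory tests. The sample size can be reproduced. For TH at 2:1, 90% power, 10 mm and SD 20: (1 + 1/2) × (1.960 + 1.282)² × (20/10)² ≈ 63.1, rounded up to 64, with 128 for Cingal as stated. Power at 128:64 is 0.904 (normal) or 0.901 (t).

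**2. Size when two visits are stacked.** The true variance of the difference between two visit means is 2σ²(1−ρ)/n, but the independence test uses 2σ²/n. True size is therefore 2[1 − Φ(1.96/√(1−ρ))].

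| ρ | 1.96/√(1−ρ) | True size |
|---|---|---|
| 0.1 | 2.07 | 3.9% |
| 0.2 | 2.19 | 2.8% |
| 0.3 | 2.34 | 1.9% |
| 0.5 | 2.77 | 0.56% |
| 0.7 | 3.58 | 0.03% |

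Binary example: 70% at both visits, φ = 0.5, n = 256. Each discordant cell has probability 0.7 × 0.3 × (1 − 0.5) = 0.105. The paired SE is √(0.21/256) = 2.9 points; the stacked SE is √(2 × 0.21/256) = 4.1 points.

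Simulated size of stacked Fisher (10,000 data sets, 70% at both visits), for φ = 0, 0.2, 0.3, 0.5, 0.7:
- n = 256: 4.4%, 2.2%, 1.3%, 0.4%, 0.0%.
- n = 64: 3.2%, 1.5%, 1.2%, 0.2%, 0.0%.

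**3. Power when stacked.** Simulated, independence test versus paired test:

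| Comparison | n | 0.3 | 0.5 | 0.7 |
|---|---|---|---|---|
| 70% to 60%, Fisher vs exact McNemar | 256 | 65 vs 77% | 67 vs 90% | 72 vs 99% |
| same | 64 | 13 vs 22% | 9 vs 29% | 5 vs 45% |
| 5 mm, two-sample t vs paired t | 256 | 85 vs 92% | 89 vs 98% | 94 vs 100% |
| same | 64 | 25 vs 38% | 22 vs 51% | 16 vs 72% |
| 3 mm, two-sample t vs paired t | 256 | 37 vs 52% | 36 vs 67% | 31 vs 87% |

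For the responder fall, Fisher keeps 65/77 = 84%, 67/90 = 74% and 72/99 = 73% of McNemar's power at n = 256. At n = 64 it keeps 13/22 = 59%, 9/29 = 31% and 5/45 = 11%. The relative loss is largest in the TH arm.

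**4. Fisher on the cross-table.** The SAP does not say which table is formed. If week-A status is crossed with week-B status in the same subjects, Fisher tests whether the two are associated. With n = 256 and no change in rate, it rejected 85% of the time at φ = 0.2, 99.6% at 0.3 and 100% at 0.5 (1,000 data sets). With a true fall from 70% to 60% the figures are nearly the same: 88%, 99.5% and 100%. The result follows the correlation and says almost nothing about change.

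**5. Change from baseline at one visit.** The response is already a within-subject difference. Testing the Cingal mean change against zero in an unadjusted change-score ANOVA gave a simulated size of 5.8%, 4.9% and 5.2% at ρ = 0.3, 0.5 and 0.7 (3,000 data sets). With baseline as covariate, as in the SAP 4.1.3 code, it was 8.6%, 6.6% and 6.0%. That excess arises because the model treats the baseline mean as fixed. It is a separate matter and runs in the other direction.

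**The case against.** The strongest reply is that no faulty test is actually scheduled. The comparisons are only permitted, and the one model shown is a single-visit analysis of change from baseline. The term analysis of variance does not rule out a subject term. On the discrete side the reach is narrow: treatment failure is one cumulative status per subject, and rescue-medication use between visits is compared descriptively, which leaves mainly OMERACT-OARSI response. All of this stands and limits the point. It does not remove it. The scope sentence expressly admits within-group and time-point comparisons, the method sentences make no exception for them, and the SAP's own account of its contrasts is a two-sample test. GEE and the mixed models serve other purposes.

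Three stronger readings are tempting, and the documents do not support them:
- A reader might infer that the plan would conceal a loss of benefit between weeks 26 and 39. Neither document names that within-arm test or gives it as the purpose. The stated objective is efficacy and safety at 39 weeks, and the primary and secondary comparisons are Cingal against TH. In a 256-subject arm the stacked tests would still detect a 70% to 60% fall with 65 to 72% power, and a 5 mm change with 85 to 94%, at correlations of 0.3 to 0.7.
- A reader might infer that the tests are always far too conservative. At correlation 0.1 to 0.2 the effect is mild, and on the cross-table Fisher errs in the opposite direction.
- A reader might infer that all within-group confidence intervals are too wide. Those for change from baseline at one visit are not widened by this problem.

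**Conclusion.** The point holds in limited form. For visit-to-visit comparisons on the same subjects, the stated methods do not give a valid test of change: stacked Fisher tests and two-sample contrasts ignore the pairing, and Fisher on the cross-table answers a different question. The size of the error under stacking depends wholly on a correlation the documents do not give, from slight at 0.1 to severe at 0.5 and above. The power figures also rest on assumed responder rates and changes and on complete pairing at the planned arm sizes; because joining the extension is optional, actual numbers may be lower. Severity is low. Only optional exploratory results are touched.

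**What to change.** In SAP 4.1.4, with a matching line in Protocol 12.1.3:
- Limit Fisher's exact test and the ANOVA contrasts to between-group comparisons at a single visit.
- For within-group comparisons of a discrete variable between visits, specify McNemar's test (or GEE), reported with the paired difference in proportions and its 95% confidence interval.
- For within-group comparisons of a continuous variable between visits, specify a paired t-test or visit contrasts from a repeated-measures mixed model.

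The choice between McNemar and GEE, or between the paired t-test and the mixed model, is a matter of preference; what matters is that one is named in advance. The cost is two sentences in the SAP, a corresponding protocol line at the next amendment, and minor programming. No new data are needed.

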10.2.14 EuroQoL EQ-5D

Outcomes information from the subject-completed EuroQol EQ-5D will be obtained at the 39-week follow up specified in Section 10.1, Schedule of Events. The EQ-5D is a standardized measure of health status developed by the EuroQol Group which is applicable to a wide range of health conditions

and treatments. The EQ-5D provides a simple descriptive profile and a single index value for health status that can be used in the clinical and economic evaluation of health care as well as in population health surveys [15].

The EQ-5D is designed for self-completion by respondents and consists of 2 pages - the EQ-5D descriptive system and the EQ visual analog scale (EQ VAS). The EQ-5D descriptive system comprises the following 5 dimensions: mobility, self-care, usual activities, pain/discomfort and anxiety/depression [15]. The subject is asked to indicate his/her health state by ticking (or placing a cross) in the box against the most appropriate statement in each of the 5 dimensions. The EQ VAS records the subject's self-rated health on a vertical VAS where the endpoints are labeled 'Best health you can imagine' and 'Worst health you can imagine' as shown in Appendix 3. This information is used as a quantitative measure of health outcome as judged by the individual respondents [15].

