Appendix 3 EQ-5D

Under each heading, please tick the ONE box that best describes your health TODAY

MOBILITY

- I have no problems in walking about
- I have slight problems in walking about
- I have moderate problems in walking about
- I have severe problems in walking about
- I am unable to walk about

SELF-CARE

- I have no problems washing or dressing myself
- I have slight problems washing or dressing myself
- I have moderate problems washing or dressing myself
- I have severe problems washing or dressing myself
- I am unable to wash or dress myself

USUAL ACTIVITIES (e.g. work, study, housework, family or leisure activities)

- I have no problems doing my usual activities
- I have slight problems doing my usual activities
- I have moderate problems doing my usual activities
- I have severe problems doing my usual activities
- I am unable to do my usual activities

PAIN / DISCOMFORT

- I have no pain or discomfort
- I have slight pain or discomfort
- I have moderate pain or discomfort
- I have severe pain or discomfort
- I have extreme pain or discomfort

ANXIETY / DEPRESSION

[figure not shown]
- I am not anxious or depressed
- I am slightly anxious or depressed
- I am moderately anxious or depressed
- I am severely anxious or depressed
- I am extremely anxious or depressed

UK (English) v.2 © 2009 EuroQol Group. EQ-5D™ is a trade mark of the EuroQol Group

- We would like to know how good or bad your health is TODAY.
- This scale is numbered from 0 to 100.
- 100 means the best health you can imagine.
0 means the worst health you can imagine.
- Mark an X on the scale to indicate how your health is TODAY.
- Now, please write the number you marked on the scale in the box below.

YOUR HEALTH TODAY =

The best health
you can imagine

UK (English) v.2 © 2009 EuroQol Group. EQ-5D™ is a trade mark of the EuroQol Group

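### If the five-level EQ-5D dimensions are tested, the plan's rule for discrete exploratory variables ignores the order of the levels and gives up power

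*SAP*

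**What the plan says.** SAP 4.1.4 and Protocol 12.1.3 carry the same two-way rule for exploratory endpoints. For one class, "the continuous variables will be analyzed via an analysis of variance and contrasts used to assess the prescribed comparisons". For the other: "For the discrete variables, a Fisher's exact test will be used to assess the desired comparisons". There is no third route for ordered responses.

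The EQ-5D stands first in the list in both sections, with no mention of which part of it is analysed. Protocol 10.2.14 describes three possible outputs:

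- **Dimension levels.** "The EQ-5D descriptive system comprises the following 5 dimensions: mobility, self-care, usual activities, pain/discomfort and anxiety/depression". Appendix 3 gives each dimension five graded answers; the second levels, for example, are "I have slight problems in walking about" and "I have slight pain or discomfort".
- **Index value.** The instrument is said to provide a "simple descriptive profile and a single index value for health" status.
- **EQ VAS.** A 0-100 self-rating, of which the protocol says: "This information is used as a quantitative measure of health outcome as judged by the individual respondents".

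Among the other listed items, OMERACT-OARSI response and treatment failure are yes/no. Rescue pill counts are outside the testing rule: "Difference in analgesic use measured by number of pills taken between visits will be compared between treatment groups descriptively".

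**The concern.** The dimension responses are discrete, so a literal reading sends them to Fisher's exact test on a 2 x 5 table. In that form (Fisher-Freeman-Halton) the levels are treated as unordered. The p-value would be the same if the labels none, slight, moderate, severe and extreme were exchanged at random. The test spreads its sensitivity over up to four degrees of freedom, whereas the natural question is whether one arm sits lower on the scale than the other. It also gives no effect estimate and cannot use the baseline response, although the Schedule of Events collects the EuroQol at baseline.

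At stake is sensitivity. A real shift in, say, pain/discomfort or mobility between Cingal and the small TH arm would be missed more often than necessary. A significant result could also reflect a pattern across levels with no clear direction.

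**Working it through.** **1. What the plan's own figures supply.** The documents give no power, effect or level distribution for the EQ-5D. They do give arm sizes, and these reproduce. For WOMAC pain at 26 weeks (difference 10 mm, SD 20, two-sided 5%, 90% power, 2:1), n(TH) = (1 + 1/2) x (20/10)^2 x (1.960 + 1.282)^2 = 6 x 10.51 = 63.04. That rounds up to 64, with 128 for Cingal; an exact t-test calculation gives 63.7. The 253 per arm for Cingal v Monovisc at 3 weeks also reproduces (252 by normal approximation, 252.1 rounded up to 253 by exact t-test). The planned arms of 256, 256 and 64 are used below, which assumes complete week-39 data.

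**2. The two tests.** Let a_j be the count in level j in the first arm and t_j the total in level j, with N = n1 + n2.

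- Fisher-Freeman-Halton: each table has probability Π C(t_j, a_j) / C(N, n1), and p is the total probability of tables no more likely than the observed one. Reordering j changes nothing. Here p was approximated with 999 random tables per trial.
- Wilcoxon rank-sum with midranks r_j: W = Σ a_j r_j, mean n1(N+1)/2, variance n1 n2 / (N(N-1)) x [Σ t_j r_j^2 - N((N+1)/2)^2].

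**3. Assumptions.** One five-level dimension follows a proportional-odds shift. Four comparator-arm distributions (%) are assumed: 10/30/40/17/3, 20/20/20/20/20, 50/30/13/6/1 and 5/25/45/22/3. There were 1,500 simulated trials per setting, so the Monte Carlo error of a power near 50% is √(0.5 x 0.5 / 1500) = 1.3 points.

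Example of the shift: for 10/30/40/17/3 the cumulative odds are 0.111, 0.667, 4.0 and 32.3. Multiplied by 1.75 they give cumulative proportions of 16.3%, 53.8%, 87.5% and 98.3% in the Cingal arm.

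**4. Results, two-sided 5%.**

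| Odds ratio | Cingal v TH, 10/30/40/17/3: Fisher → Wilcoxon | Gap, Cingal v TH, four distributions (points) | Gap, Cingal v Monovisc, four distributions (points) |
|---|---|---|---|
| 1.3 | 12.4% → 17.5% | 3.4-8.1 | 12.9-16.1 |
| 1.5 | 22.3% → 33.7% | 6.7-16.2 | 17.7-22.5 |
| 1.75 | 42.1% → 60.4% | 12.2-18.9 | 11.7-14.5 |
| 2.0 | 59.9% → 76.3% | 10.1-18.4 | 3.4-5.5 |
| 2.5 | 86.0% → 95.1% | 6.7-11.4 | 0-0.5 |
| 3.0 | 95.7% → 98.8% | 2.3-4.6 | 0 |

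With no shift (odds ratio 1), rejection rates were 3.9-5.5% for Fisher and 4.0-5.1% for Wilcoxon over both comparisons. A repeat simulation for Cingal v TH gave gaps of about 2-7 points at 1.3, 8-19 at 1.5-2.0 and 2-5 at 3.0. Taken together the ranges are 2-8, 7-19 and 2-5.

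**5. Analytic check.** Suppose a one-degree-of-freedom test has 60% power, so its noncentrality is (1.960 + 0.253)^2 = 4.90. Spreading the same noncentrality over 3 or 4 degrees of freedom costs 16.8 or 21.1 points. The simulated 18.3 points at odds ratio 1.75 lies between these, as expected when the fifth level is nearly empty.

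**The case against.** The strongest objection is that the premise is conditional. Nothing in either document says that the dimension levels will be tested. If only the index value or the EQ VAS is analysed, the analysis-of-variance sentence applies and the problem does not arise. That stands, and the point is worded accordingly. It does not remove the point, because if the levels are tested the only prespecified test is the order-blind one.

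Two stronger readings are tempting, and the documents do not support them.

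- A reader might infer that every discrete exploratory variable is badly served. Pill counts are compared descriptively, and for yes/no variables there is no order to lose, so Fisher's exact test is suitable for responder status and treatment failure.
- A reader might take the sample-size assumption of 10 mm with SD 20 as a 0.5 SD shift on the EQ-5D and quote one power loss as a property of the plan. A simulation with latent normal shifts of 0.3-0.5 SD does give about 10-18 points, with Pearson chi-square standing in for the exact test. But the 10 mm is for WOMAC pain at week 26, and the gap is widest at effects of about that size. Outside the middle range it is much smaller.

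It is also fair to say that these comparisons are optional and outside the testing hierarchy, and that Fisher's exact test remains valid. The planned summary tables would show level counts by arm and so the direction. Finally, the simulations all use a consistent shift, which is the alternative that favours a rank test. All of this limits the importance of the point but does not reverse it.

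**Conclusion.** The concern holds in conditional form and is minor. If EQ-5D dimension levels are compared between arms, the stated rule uses a test that ignores their order and has less power against a consistent shift. At full planned numbers the loss is about 2-8 points at an odds ratio of 1.3, 7-19 at 1.5-2.0 and 2-5 at 3.0 for Cingal v TH, and about 0-23 points for Cingal v Monovisc.

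These sizes rest on assumed level distributions, a common odds ratio and complete week-39 data. Entry to the extension is optional (Protocol synopsis, Sample Size), so achieved numbers and both powers may be lower. The cost is in power and interpretability: type I error is about 5% either way, and no primary or secondary test changes.

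**What to change.** In both SAP 4.1.4 and Protocol 12.1.3:

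1. Limit Fisher's exact test to binary variables (OMERACT-OARSI response, treatment failure).
2. State which EQ-5D components are analysed: dimension levels, index value, EQ VAS, or a named subset.
3. For any ordered dimension levels, prespecify either a Wilcoxon rank-sum test or a proportional-odds model adjusted for the baseline level. With the model, report the common odds ratio and its 95% CI.

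The cost is a sentence or two in each document and a different SAS procedure. No new data are needed, since the EuroQol is already scheduled at baseline and at 39 weeks. There are two drawbacks: the proportional-odds model assumes one odds ratio across all levels, and a rank test is less sensitive to differences that do not run in one direction. Making the choice before analysis avoids selecting a test after seeing the data.
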